#### 11.5.1.3. Study and Treatment Completion

Study and Treatment Completion Definitions

 
• A subject is considered to have completed the treatment period if they have not prematurely discontinued IP and attended Visit 7.
 
• A subject is considered to have completed the study if they either attended Visit 7 or had a phone contact at Visit 7.
 

#### 11.5.1.4. Projected Week 52 Date

For those subjects who have withdrawn from the study prior to Week 52, a projected Week 52 date will be derived as follows:

Projected Week 52 Date = Date of randomisation + 52 weeks

#### 11.5.1.5. At Risk Period for Calculation of Raw Event Rate

##### 11.5.1.5.1. All Cause Mortality

For calculations of raw event rate the 'at risk period' in years (used for the denominator) will be defined as follows:

- On-treatment at risk period:
  - For subjects that completed the study up to Week 52 the on-treatment at risk period will derived as:  
(minimum (date of end of study treatment + 7, date of death, date of study conclusion) – date of start of treatment + 1)/365.25
  - For subjects that prematurely withdrew from the study prior to Week 52 and that have a survival status reported the on-treatment at risk period will derived as:  
(minimum (date of end of study treatment + 7, date of death, date last known alive) – date of start of treatment + 1)/365.25
  - For subjects that prematurely withdrew from the study prior to Week 52 and that do not have a survival status reported the on-treatment at risk period will derived as:  
(minimum (date of end of study treatment + 7, date of death, date of study conclusion) – date of start of treatment + 1)/365.25
- On and off-treatment at risk period:
  - For subjects that did not prematurely discontinue study treatment the on and off-treatment at risk period will derived as:  
(minimum (date of end of study treatment + 7, date of death, date of study conclusion) – date of start of treatment + 1)/365.25
  - For subjects that prematurely discontinued the study treatment period and completed the study up to Week 52 the on and off-treatment at risk period will derived as:  
(Date of study conclusion – date of start of treatment + 1)/365.25
  - For subjects that prematurely discontinued the study treatment period and prematurely withdrew from the study prior to Week 52 the on and off-treatment at risk period will derived as  
(minimum(Date last known alive, Date of Death, Projected date of Week 52 (as defined in Section 11.5.1.4) + 7) – date of start of treatment + 1)/365.25
  - For subjects that prematurely withdrew from the study prior to Week 52 and that do not have a survival status reported the on and off-treatment at risk period will derived as:  
(Date of study conclusion – date of start of treatment + 1)/365.25

#### **11.5.1.5.2. Other Data**

For calculations of raw event rate the ‘at risk period’ in years (used for the denominator) will be defined as follows:

- On-treatment at risk period:
  - (minimum (date of end of study treatment+1, date of death, date of study conclusion) – date of start of treatment + 1)/365.25
- Post-treatment at risk period:
  - if date of study conclusion > date of end of treatment as follows:  
(date of study conclusion – date of end of treatment - 1)/365.25
  - Else post-treatment at risk period will be set to 0

**11.5.2. Study Population**

**11.5.2.1. Demographics**

Demographics
Age

 
• Age will be calculated based on the Pre-Screening Visit date (or Screening, if pre-screening not performed).
 
• Only year of birth is collected on the eCRF, therefore day and month of birth are imputed as '30JUN' in order to derive age.
 
• Birth date will be presented in listings as 'YYYY'.
 

Age Category

 
• Age categories are based on age as derived above and are defined as:                             
 
○ ≤ 64 years
 
○ 65 - 74 years
 
○ 75 – 84 years
 
○ ≥ 85 years
 
 
 

**11.5.2.2. Subject Disposition**

Subject Disposition

 
• For Kaplan-Meier plots of study withdrawal over time and discontinuation from study treatment over time, censoring will be performed as follows:                             
 
○ For study withdrawal, subjects are represented from their Day 1 date to the date of early withdrawal from the study (or date of death). Subjects that completed the study are censored at the earliest of the date of completion and Day 365.
 
○ For discontinuation from study treatment, subjects are represented from their Day 1 date to the date of discontinuation from study treatment (or date of death). Subjects that complete study treatment per protocol are censored at the earliest of their study treatment stop date and Day 365.
 
 
 

**11.5.2.3. Treatment Compliance**

Treatment Compliance

 
● If a dose counter start count is missing then it will be assumed to be 30. If any dose counter stop is missing then the treatment compliance will be set to missing for that subject.
 
● Number of doses of study treatment taken by each subject from each inhaler = dose counter start- dose counter stop. 
 
○ Compliance=sum of (dose counter start–dose counter stop) from each inhaler x 100 / (treatment stop date – treatment start date +1)
 
 
 
● Compliance will be categorized as follows: 
 
< 80 %
 
≥ 80 % to < 95 %
 
≥ 95 % to ≤105 %
 
>105 % to ≤120 %
 
>120 %
 
 
 
● If a subject received a treatment other than the randomized treatment during the study, the compliance will still be calculated using data from all containers received and overall treatment start and stop dates.
 

**11.5.2.4. Cardiovascular Risk Factors**

Cardiovascular Risk Factors

 
● Subjects with at least one of the following current or past medical conditions at Screening will be classed as having a cardiovascular (CV) risk factor. The number of CV risk factors at Screening (0, 1, or >=2) will be derived. 
 
● Angina pectoris
 
● Coronary artery disease
 
● Myocardial infarction
 
● Arrhythmia
 
● Congestive heart failure
 
● Hypertension
 
● Cerebrovascular accident
 
● Carotid or aorto-femoral vascular disease
 
● Diabetes mellitus
 
● Hypercholesterolemia
 
 
 

**11.5.2.5. Pneumonia Risk Factors**

Pneumonia Risk Factors at Screening

 
● The following categories will be summarized to identify pneumonia risk factors: 
 
● Age (<65, ≥65)
 
● Gender
 
● BMI (will be defined twice; <21 kg/m^2, ≥21 kg/m^2; <25 kg/m^2, ≥25 kg/m^2)
 
 
 

**Pneumonia Risk Factors at Screening**

- Smoking status at screening
- Pneumonia history
- GOLD Grade

**11.5.2.6. Concomitant Medications****Concomitant Medications****COPD Concomitant Medications**

- COPD concomitant medications will be grouped into the following RMCs based on pre-defined code lists derived from ATC classifications:
  - Antiinfectives (antibiotics, antifungals, antivirals, antiseptics)
  - Short-acting anticholinergic
  - Short-acting beta-2 agonist
  - Long-acting anticholinergic
  - Long-acting beta-2 agonist
  - Xanthine
  - PDE4 inhibitor
  - Corticosteroid – inhaled
  - Corticosteroid – depot
  - Corticosteroid - systemic oral parenteral and intra-articular
  - Corticosteroid – other
  - Leukotriene receptor antagonist
  - Nedocromil or cromolyn sodium
  - Mucolytic
  - Oxygen
  - Other medication given for exacerbation
  - Other COPD medication

**COPD Medication Combination**

- COPD medications taken on the day of the Screening visit and at IP discontinuation will be grouped into the following categories based on the RMC classification:
  - ICS
  - LABA
  - LAMA
  - Xanthine
  - PDE4 Inhibitors
  - Any combination of the above
  - No selected RMC medication combination
- COPD medication combinations taken at study treatment discontinuation for subjects that provided post-treatment information will include all subjects that prematurely discontinued study treatment.

**11.5.2.7. Smoking Status****Smoking Status**

- Smoking Status at Screening is determined directly from the eCRF.
- A subject's smoking status from Visit 2 (Day 1) onwards will be derived from the smoking status at the visit in question and any changes in smoking status from the time of the previous assessment (e.g., date of any changes in status were made).
- Only smoking status responses recorded at scheduled visits will be included in the summary tables.

**11.5.2.8. COPD Exacerbation History****COPD Exacerbation History**

- Individual exacerbations during the 12 months prior to Screening and during the study were to be collected on the eCRF by the Investigator.
- COPD exacerbations with onset date on or after the date of Screening will not be included in the counts of number of exacerbations in the past year; all other exacerbations recorded on the eCRF will be included in the counts, even if onset/resolution dates are missing or earlier than the start of the exact 12 month period prior to Screening.
- COPD exacerbations reported in the past 12 months will be categorized as 0, 1, 2,  $\geq 3$  and a separate category of  $\geq 2$ .
- Number of COPD exacerbations reported in the past 12 months prior to Screening will be summarized according to three categories: moderate COPD exacerbations, severe COPD exacerbations and moderate/severe COPD exacerbations. Exacerbation severity is defined in Section [11.5.3.1](#).
- Total number of moderate/severe COPD exacerbations are defined as total numbers of moderate and severe COPD exacerbations for each subject.
- Summaries of moderate/severe exacerbations by treatment course are defined as exacerbations treated with systemic/oral corticosteroids (with or without antibiotics), and exacerbations treated with antibiotics (with or without systemic/oral corticosteroids).

**11.5.2.9. Screening Lung Function and GOLD Grade****Screening Lung Function****Pre-bronchodilator FEV1/FVC, FEV1 Percent Predicted and Reversibility**

- Pre-bronchodilator FEV1/FVC ratio and pre-bronchodilator FEV1 as a percentage of predicted normal at Screening are not collected in the eCRF and will be calculated as:
  - Pre-bronchodilator FEV1/FVC = Pre-bronchodilator FEV1/Pre-bronchodilator FVC
  - Pre-bronchodilator Percent Predicted = (Pre-bronchodilator FEV1/Predicted FEV1) \* 100
- The reversibility to salbutamol status of a subject is calculated at Screening and is based on the

Screening Lung Function
Pre-bronchodilator FEV1/FVC, FEV1 Percent Predicted and Reversibility

difference (absolute change and % change) between a subject's pre-salbutamol assessment of FEV1 and their post-salbutamol assessment of FEV1 and is defined as follows:
 
 
○ Reversible, if they had a difference in FEV1 of <math>\geq 12\%</math> and <math>\geq 200</math> mL, or
 
○ Non-reversible, if they had a difference in FEV1 of <math><200</math> mL or a <math>\geq 200</math> mL difference that was <math><12\%</math> of the pre-salbutamol FEV1.
 

GOLD Grade 1-4 at Screening

 
● Subjects will be classified into Global Initiative on Obstructive Lung Disease (GOLD) Grades 1-4 using the post-salbutamol percent predicted FEV1 assessment at Screening: 
 
○ GOLD Grade 1 (Mild): percent predicted FEV1 <math>\geq 80\%</math>
 
○ GOLD Grade 2 (Moderate): <math>50\% \leq</math> percent predicted FEV1 <math>< 80\%</math>
 
○ GOLD Grade 3 (Severe): <math>30\% \leq</math> percent predicted FEV1 <math>< 50\%</math>
 
○ GOLD Grade 4 (Very Severe): percent predicted FEV1 <math>< 30\%</math>
 
 
 

**11.5.3. Efficacy and Health Outcomes**

**11.5.3.1. Exacerbations**

COPD Exacerbations
General

 
● Each COPD exacerbation will be categorized based on severity as follows: 
 
○ Mild: no treatment with systemic/oral corticosteroids and/or antibiotics and no hospitalization and that did not result in death
 
○ Moderate: required treatment with systemic/oral corticosteroids and/or antibiotics (not involving hospitalization or resulting in death)
 
○ Severe: required hospitalization or resulted in death
 
 
 
● The duration of an exacerbation will be calculated as exacerbation resolution date or date of death - exacerbation onset date + 1.
 
● Summaries of moderate/severe exacerbations by treatment course are defined as exacerbations treated with systemic/oral corticosteroids (with or without antibiotics), and exacerbations treated with antibiotics (with or without systemic/oral corticosteroids).
 
● The raw event rate per thousand subject-years for exacerbations will be calculated as the number of events x 1000 divided by the at risk period during the time-period of interest as defined in Section 11.5.1.5.2
 
● For the boxplot of on-treatment moderate/severe annual raw COPD exacerbation rates the individual subject rate will be derived as number of events experienced by the subject x 1000 divided by the individual subject's on-treatment at risk period as defined in Section 11.5.1.5.2.
 

**COPD Exacerbations****Offset variable for rate of exacerbations**

For analyses of rate of moderate/severe COPD exacerbations, the offset variable will be defined as follows:

- Including on-treatment data only
  - logarithm of (on-treatment at risk period, as defined in Section 11.5.1.5.2)
- Including both on and off-treatment data
  - logarithm of ([total time in study per subject (defined in Section 11.5.4.1)]/365.25).
- Jump to reference (using on-treatment data)
  - For subjects that complete study treatment:  
logarithm of (on-treatment at risk period, as defined in Section 11.5.1.5.2)
  - For subjects that prematurely discontinue study treatment but complete the study up to Week 52:  
logarithm of ([Actual date of Week 52 – date of start of treatment + 1]/365.25)
  - For subjects that prematurely discontinue from study treatment and withdraw from the study prior to Week 52:  
logarithm of ([Projected Week 52 date (as defined in Section 11.5.1.4) – date of start of treatment + 1]/365.25)
- Jump to reference (using on and off-treatment data)
  - For subjects that complete study treatment:  
logarithm of ([total time in study per subject (defined in Section 11.5.4.1)]/365.25)
  - For subjects that prematurely discontinue study treatment but complete the study up to Week 52:  
logarithm of ([Actual date of Week 52 – date of start of treatment + 1]/365.25)
  - For subjects that prematurely discontinue from study treatment and withdraw from the study prior to Week 52:  
logarithm of ([Projected Week 52 date (as defined in Section 11.5.1.4) – date of start of treatment + 1]/365.25)

**Time to First On-treatment Exacerbation**

- The time to first on-treatment exacerbation will be calculated as exacerbation onset date of first on-treatment exacerbation – date of start of treatment + 1.
- Subjects will be represented from their Day 1 date to the start date of their first exacerbation or date of censoring. Subjects that have not experienced an on-treatment exacerbation are censored at the earliest of the date of their treatment stop date +1 day or the date of death.

COPD Exacerbations
Time to First Exacerbation Including Off-treatment data

 
The time to first exacerbation including off-treatment data will be calculated as exacerbation onset date of first exacerbation – date of start of treatment + 1.
 
Only exacerbations reported during the on-treatment and post-treatment study phases will be considered (see Section 11.3.3 for details of assigning study phase)
 
Subjects will be represented from their Day 1 date to the start date of their first exacerbation or date of censoring. Subjects that have not experienced an on or off-treatment exacerbation are censored at the earliest of (date of study conclusion or the date of death).
 

Time to First On-treatment Moderate/severe Exacerbation or Premature Study Treatment Discontinuation

 
The time to first on-treatment moderate/severe exacerbation will be calculated as exacerbation onset date of first on-treatment moderate/severe exacerbation – date of start of treatment + 1.
 
The time to study treatment discontinuation will be calculated as the date of premature study treatment discontinuation – date of start of treatment + 1.
 
The time to first on-treatment moderate/severe exacerbation or study treatment discontinuation is defined as the earliest of the time to first on-treatment moderate/severe exacerbation or time to premature study treatment discontinuation.
 
Subjects will be represented from their Day 1 date to the earliest of the event or censoring. Subjects who do not experience the event will be censored at the earliest of the date of their treatment stop date +1 day or the date of death.
 

Time to Each On-treatment Exacerbation

 
Subjects will be defined as at risk while on treatment from the start of treatment until their first exacerbation, and then from the day after each exacerbation had resolved.
 
Subjects will be represented from their study treatment start date to the earliest of the date of their treatment stop date +1 day or the date of death.
 

Association to Chest X-Ray

 
A chest X-ray is considered associated with an exacerbation if it is performed within the duration of the exacerbation or performed between -7 days to +10 days (inclusive) of the onset date of the exacerbation.
 

### 11.5.3.2. Lung Function

Spirometry
Trough FEV1 and FVC

 
The trough value for FEV1 and FVC at Weeks 4, 16, 28, 40 and 52 visit is the pre-dose (prior to taking the morning dose of study treatment) and pre-bronchodilator assessment at that visit.
 

Spirometry
Post-Bronchodilator FEV1 and FVC

 
The post-bronchodilator value for FEV1 and FVC at Weeks 4, 16, 28, 40 and 52 is the pre-dose (prior to taking the morning dose of study treatment), post-bronchodilator assessment (approximately 10 to 30 minutes after administering four puffs of salbutamol).
 

FEV1 Reversibility (mL)

 
The reversibility to salbutamol is calculated at each visit where FEV1 is collected as follows:  <math display="block">\text{FEV1 reversibility (mL)} = \text{post-salbutamol FEV1 (mL)} - \text{pre-salbutamol FEV1 (mL)}</math> 
 

### 11.5.3.3. SGRQ

St. George's Respiratory Questionnaire for COPD Patients (SGRQ-C)
General

 
The SGRQ-C contains 14 questions with a total of 40 items grouped into three domains (Symptoms, Activity and Impacts).
 
Details for how to score the SGRQ-C, including handling of missing data or multiple responses to questions, are outlined in the SGRQ-C manual (Jones, 2016).
 
SGRQ-C domain and total scores will be converted to SGRQ scores as described in the manual.
 
Changes from baseline in domain and total score will be calculated for the converted scores.
 
If the language of the SGRQ-C conducted at a post-treatment visit is different to the language used at Day 1 baseline, all SGRQ scores at that visit and all subsequent visits will be set to missing.
 

Responder Status according to SGRQ Total Score

 
A subject will be considered a responder according to SGRQ total score if their on-treatment SGRQ total score has decreased at least 4 units from the baseline SGRQ total score.
 
A subject will be considered a non-responder if their on-treatment SGRQ total score has decreased by less than 4 units, has not changed, or has increased compared to baseline.
 
Moderate and major response will be defined using cut-offs determined as follows: 
 
Cut-off for defining moderate responder will use the integer value of the mean change from baseline in SGRQ total score at Week 52 for all subjects (combined treatment groups) who rated 'better' in the subject global rating of change in COPD severity at Week 52.
 
Cut-off for defining major responder will use the integer value of the mean change from baseline in SGRQ total score at Week 52 for all subjects (combined treatment groups) who rated 'much better' in the subject global rating of change in COPD severity at Week 52.
 
 
 
A subject will be considered a major responder if their on-treatment change from baseline in SGRQ total score is <math>\leq</math> the cut-off value for major responder.
 
A subject will be considered a moderate or major responder if their on-treatment change from
 

St. George’s Respiratory Questionnaire for COPD Patients (SGRQ-C)
baseline in SGRQ total score is $\leq$ the cut-off value for moderate responder.

 
Missing data will be handled as detailed in Section 11.6.
 

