**11.5.3.4. CAT**

COPD Assessment Test (CAT)
CAT Score

 
The CAT consists of eight items each formatted as a six-point differential scale: 0 (no impact) to 5 (high impact). A CAT score will be calculated by summing the non-missing scores on the eight items with a range from 0 to 40.
 
If one item is missing, then the score for that item is set as the average of the non-missing items. If more than one item is missing, then the CAT score will be set to missing.
 
If the language of the CAT conducted at a post-baseline visit is different to the language used at Day 1 baseline, the CAT score for that visit and all subsequent visits will be set to missing.
 
If there is more than one response to a question at a visit or duplicate questionnaires, the CAT score for that visit will be set to missing.
 

Responder Status according to CAT Score

 
A subject will be considered a responder according to CAT score if their on-treatment CAT score has decreased at least 2 units from the baseline CAT total score.
 
A subject will be considered a non-responder if their on-treatment CAT score has decreased by less than 2 units, has not changed, or has increased compared to baseline.
 
Missing data will be handled as detailed in Section 11.6.
 

CAT Score Categories
The CAT score categories will be defined as: 
 
A score < 10
 
A score <math>\geq</math> 10
 

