**11.5.3.6. BDI/TDI**

**BDI/TDI**

**General**

- The BDI focal score will be calculated as the sum of the ratings recorded for each of the three individual scales (Functional Impairment, Magnitude of Task, and Magnitude of Effort). Each of these scales has five possible scores ranging from 0 to 4 (with lower scores indicating more impairment), with the range of the BDI focal score 0 to 12. If a score is missing for any of the three scales, then the BDI focal score will be set to missing. BDI is assessed at baseline (Day 1).
- The TDI focal score will be calculated as the sum of the ratings recorded for each of the three individual scales (Functional Impairment, Magnitude of Task, and Magnitude of Effort). Each of these scales has a possible score ranging from -6 (major deterioration) to +6 (major improvement). TDI focal score is calculated as the sum of the three individual scores and then

BDI/TDI

divided by 2 (so the range of the TDI focal score is -9 to +9). If a score is missing for any of the three scales, then the TDI focal score will be set to missing.
 
 
• If the language of the TDI conducted at a visit is different to the language for the BDI, all TDI scores at that visit and subsequent visits will be set to missing.
 
• If there is more than one response to a question at a visit or duplicate questionnaires, the BDI or TDI score for that visit will be set to missing.
 

Categorization of TDI Focal Score

 
• Full categorization of TDI focal score for categorical summary is as follows: 
 
‘major improvement’ defined as a score of <math>\geq 7</math> to <math>\leq 9</math>
 
‘moderate improvement’ defined as a score of <math>\geq 4</math> to <math>< 7</math>
 
‘minor improvement’ defined as a score of <math>\geq 1</math> to <math>< 4</math>
 
‘no change’ defined as a score of <math>> -1</math> to <math>< 1</math>
 
‘minor deterioration’ defined as a score of <math>> -4</math> to <math>\leq -1</math>,
 
‘moderate deterioration’ defined as a score of <math>> -7</math> to <math>\leq -4</math>
 
‘major deterioration’ defined as a score of <math>\geq -9</math> to <math>\leq -7</math>
 
 
 

Responder Status according to TDI Focal Score

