**11.5.3.8. EQ-5D-5L**

EQ-5D-5L

 
• If the language of the EQ-5D-5L conducted at a post-baseline visit is different to the language used at baseline, the EQ-5D-5L scores for that visit and all subsequent visits will be set to
 

missing.

- If there is more than one response to a question at a visit or duplicate questionnaires, the EQ-5D-5L health state and utility score for that visit will be set to missing.

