## 11.6. Appendix 6: Handling of Missing Data

Element	Reporting Detail
General	
 
• Missing data occurs when any requested data is not provided, leading to blank fields on the collection instrument:               
 
○ These data will be indicated by the use of a “blank” in subject listing displays unless all data for a specific visit are missing in which case the visit is not displayed in the listing.
 
○ Answers such as “Not applicable” and “Not evaluable” are not considered to be missing data and will be displayed as such.
 
○ Missing data will generally not be considered in the calculation of percentages (i.e., the denominator will not include subjects who have missing data at a given time point).
 
○ No imputation will be made for any missing numerical data, except in the specified sensitivity analyses of the primary and secondary endpoints to assess the impact of missing data on study results.
 
 
 

Responder	
 
• Subjects with a missing baseline will have responder status as missing.
 
• Subjects with missing on-treatment data and a subsequent non-missing on-treatment scheduled assessment will not be considered a responder or non-responder but will be left as missing.
 
• Subjects that have withdrawn from study treatment prior to the visit in question will be imputed as non-responders at all visits post-study treatment discontinuation where the assessment was expected to be performed (regardless of whether the subject has had a post-treatment assessment performed or not). This includes all visits up to and including Week 52.
 
• Subjects with missing on-treatment data and no subsequent non-missing on-treatment scheduled assessments will be imputed as non-responders.
 

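### A questionnaire completed in the wrong language voids all later scores of that instrument, including valid ones, and for SGRQ, CAT and TDI this probably codes an on-treatment subject as a non-responder; the effect is small and the correction nearly free.

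*SAP*

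**What the plan says.** SAP 11.5.3 has a separate language rule for each instrument.

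- **SGRQ (11.5.3.3).** The trigger is "If the language of the SGRQ-C conducted at a post-treatment visit is different to the language used at Day 1 baseline". The consequence is that "all SGRQ scores at that visit and all subsequent visits will be set to missing".
- **CAT (11.5.3.4).** After a mismatch at a post-baseline visit, "the CAT score for that visit and all subsequent visits will be set to missing".
- **TDI (11.5.3.6).** The comparison is with the BDI language, and "all TDI scores at that visit and subsequent visits will be set to missing".
- **EQ-5D-5L (11.5.3.8).** After a mismatch at a post-baseline visit, the SAP voids "the EQ-5D-5L scores for that visit and all subsequent visits".

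Duplicate forms or multiple answers are treated more narrowly. For CAT, "the CAT score for that visit will be set to missing", and TDI and EQ-5D-5L likewise lose only the affected visit.

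The responder definitions for SGRQ, CAT and TDI refer missing data to SAP 11.6. There, a gap followed by a later on-treatment assessment stays missing. Otherwise: "Subjects with missing on-treatment data and no subsequent non-missing on-treatment scheduled assessments will be imputed as non-responders".

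SGRQ, CAT and TDI are scheduled at Weeks 4, 28 and 52 after Day 1, and EQ-5D-5L at Weeks 28 and 52. Change from baseline in SGRQ at Week 52 against FF/VI is a secondary endpoint with a multiplicity-adjusted p-value (SAP 8.2.1). The SGRQ, CAT and TDI responder analyses are other efficacy endpoints with unadjusted p-values (SAP 2.2 and 9.1.2.7). EQ-5D-5L is only summarised (SAP 9.1.1.7).

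**The concern.** The evident reason to drop a wrong-language score is that its change from baseline compares two language versions. A later form in the baseline language does not have that problem. Extending the deletion to all later visits therefore adds protection in no case. If the subject stays in the new language, a visit-by-visit rule voids those visits anyway. The extra scores removed are those from forms back in the baseline language.

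The deletion also interacts badly with SAP 11.6. That section distinguishes an intermittent gap, left missing, from a terminal one, counted as non-response. Voiding every later visit makes an intermittent gap look terminal, so a form-handling error is recorded as treatment failure in a subject who may have improved. The SGRQ responder table (2.069) is among the displays marked as headline results.

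For the SGRQ secondary endpoint, observed Week 52 scores are withheld from the MMRM. In the jump-to-reference analysis (SAP 8.2.2.1, extended there to SGRQ), missing on-treatment values are imputed from the reference arm. A subject still taking FF/UMEC/VI would be treated as if on the comparator although a valid score is on file.

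**Working it through.** The plan states no figure to reproduce. The check is a trace of the rules, followed by an illustration of size.

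**1. Trace.** Inputs: the visit schedule (Weeks 4, 28, 52), the language rules in 11.5.3, and the responder rules in 11.6. Take a subject who stays on treatment, completes one instrument in the wrong language at one visit only, and is otherwise fully observed. NR means coded as a non-responder.

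| Wrong language at | SAP rule: Week 4 / 28 / 52 | Void that visit only: Week 4 / 28 / 52 |
|---|---|---|
| Week 4 | NR / NR / NR | left missing / observed / observed |
| Week 28 | observed / NR / NR | observed / left missing / observed |
| Week 52 | observed / observed / NR | observed / observed / NR |

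A mismatch at Week 4 costs three of three post-baseline scores under the SAP rule and one of three under a visit-only rule. A mismatch at Week 52 gives the same result either way, so narrowing the language rule does not settle that case; 11.6 must address it. For EQ-5D-5L, a mismatch at Week 28 removes a valid Week 52 score, with no responder consequence.

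**2. Number of subjects (assumed).** Let f be the share of subjects affected. With f = 0.5% to 2% in an arm of 4,000:

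- 4,000 × 0.005 = 20
- 4,000 × 0.02 = 80

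This is an upper bound for those rates. It requires every mismatch to be at Week 4 or 28, every subject to return to the baseline language, and every subject to remain on treatment with a Week 52 form.

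**3. Responder rate and odds ratio (assumed).** If a share f is forced to non-response regardless of true status, a responder rate p becomes p(1 − f). At p = 40%, the loss is 0.40 × 0.5% = 0.2 to 0.40 × 2% = 0.8 percentage points.

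With assumed Week 52 rates of 40% and 34%, the odds ratio is (0.40/0.60) / (0.34/0.66) = 1.294. At f = 2% in both arms the rates become 39.2% and 33.32%, and the odds ratio is (0.392/0.608) / (0.3332/0.6668) = 1.290.

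| f | Odds ratio, both arms affected | Odds ratio, only the 40% arm affected |
|---|---|---|
| 0 | 1.294 | 1.294 |
| 0.5% | 1.293 | 1.283 |
| 1% | 1.292 | 1.273 |
| 2% | 1.290 | 1.252 |
| 5% | 1.285 | 1.190 |

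**4. SGRQ MMRM.** Losing a share f of Week 52 scores in both arms inflates the standard error by about 1/√(1 − f). At f = 2% this is 1/√0.98 = 1.010, or about 1%.

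**The case against.** The best defence is that the rule looks deliberate. For CAT, TDI and EQ-5D-5L, the SAP separates duplicate answers (that visit only) from language mismatch (that visit and later ones). The convention is prespecified and applied without regard to treatment, and counting unobserved data as non-response is a common conservative choice. That shows consistency, but the documents give no reason for deleting scores in the baseline language.

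It is also fair that the harmful pattern, a single-visit switch followed by a return, is not shown to occur. SAP 11.2.1 indicates electronic capture of questionnaires, which may make such slips rare. If a change of language persists, or first happens at Week 52, the SAP rule and a visit-only rule void the same scores. This limits the size but does not supply a reason for the rule.

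Two points of wording reduce certainty. The SGRQ trigger refers to a post-treatment visit, and SAP 11.3.3.1 places the post-treatment phase after treatment has stopped. Read literally, the SGRQ rule would not touch on-treatment visits. Post-baseline, as written for CAT and EQ-5D-5L, is very probably meant. Also, SAP 11.6 describes missing data as requested data not provided, leaving blank fields, and does not expressly cover a completed form voided by derivation. Non-response is the natural reading because 11.5.3 sends missing data there, but it is not stated.

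A reader might infer more than the documents support:

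- **That one wrong-language form wipes out all four instruments.** Each rule concerns its own instrument. A wrong-language SGRQ-C leaves CAT, TDI and EQ-5D-5L untouched.
- **That EQ-5D-5L subjects become non-responders.** EQ-5D-5L has no responder status.
- **That the non-responder coding damages the test in the hierarchy.** That test is the MMRM of change in SGRQ, which does not use responder status. Scores lost through a handling error unrelated to response are compatible with its missing-at-random assumption, so the cost is mainly precision.

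**Conclusion.** The point holds as a minor defect in the derivation rules. Instrument by instrument, the SAP discards later scores in the baseline language. For SGRQ, CAT and TDI, it then most naturally codes an on-treatment subject as a non-responder from the mismatched visit through Week 52. SGRQ also loses Week 52 scores from the MMRM and would receive reference-arm imputations in the jump-to-reference analysis.

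The expected numerical effect is very small. At an assumed 0.5% to 2% of subjects affected in both arms, with assumed responder rates of 40% and 34%, the odds ratio falls from 1.294 to between 1.293 and 1.290. Neither the mismatch rate nor the responder rates are in the documents. Larger shifts need errors that are common or confined to one arm, and a double-blind trial gives no reason to expect the latter. A reader might take this as a material bias in the treatment comparison; the documents do not support that. The conclusion rests on reading the SGRQ trigger as post-baseline and on applying 11.6 to voided scores.

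**What to change.** 1. In SAP 11.5.3.3, 11.5.3.4, 11.5.3.6 and 11.5.3.8, set to missing only the visits whose language differs from the baseline (for TDI, the BDI) language. Keep later visits completed in the baseline language.
2. In 11.5.3.3, reconcile the post-treatment trigger with the post-baseline wording used for CAT and EQ-5D-5L.
3. In 11.6, state how an on-treatment score voided for language enters the responder analysis; leaving it missing, rather than counting it as non-response, fits the reason for voiding it. This also settles a mismatch at Week 52 and a persistent change of language, which step 1 does not.
4. In 8.2.2.1, state how such a score enters the jump-to-reference analysis for SGRQ.

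The cost is about one sentence per section and a simpler derivation, with no new data. It should be settled by source data lock, when the SAP requires analysis decisions to be final. Tabulating language mismatches by arm and visit would show whether the issue arose at all.
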